12.2.5 Vital signs

As vital signs, measure blood pressure (sitting), pulse rate, and body temperature.

12.2.6 CSSC(Clinical Signs and Symptoms Checklist)

Infection signs are checked using the CSSC by the investigator at each visit. In case infection signs are suspected, laboratory tests and wound culture may be additionally conducted for confirmation. In case additional tests are performed, the result should be recorded in the Case Report Form.

According to [Baranoski, Elizabeth A. Ayello, Wound Care Essentials: Practice Principles], define an infection as the development of 'Purulent exudates' or '2 or more symptoms of the CSSC'.

At every visit after the study device application, evaluate the previous infection signs as well as any newly developing infection signs.

Clinical Signs and Symptoms Checklist	
Signs and symptoms	Check (+) if present

Increasing pain in the ulcer area
 
The patient reports increased level of peri-ulcer pain since the ulcer developed. Ask him to select the most appropriate statement for current level of ulcer pain from the following choices:
 
 1. I can't detect pain in ulcer area. 2. I have less ulcer pain now than I had in the past. 3. The intensity of the ulcer pain has remained the same since the ulcer developed. 4. I have more ulcer pain now than I had in the past. 
If the patient selects number 4, his pain is increasing. Write n/a if the patient can't respond to the question.
	

Erythema
 
The presence of bright or dark red skin or darkening of normal ethnic skin color immediately adjacent to the ulcer opening indicates erythema.
	

Edema
 
The presence of shiny, taut skin or pitting impressions in the skin adjacent to the ulcer
	

Clinical Signs and Symptoms Checklist	
Signs and symptoms	Check (+) if present
but within 4cm from the ulcer margin indicates edema. Assess pitting edema by firmly pressing the skin within 4cm of ulcer margin with a finger, release and waiting 5 seconds to observe indentation.	
Heat A detectable increase in temperature of the skin adjacent to the ulcer but within 4cm of the ulcer margin as compared to the skin 10cm proximal to the wound indicates heat. Assess differences in skin temperature using the back of your hand or your wrist.	
Purulent exudates Tan, creamy, yellow, or green, thick fluid that's present on a dry gauze dressing removed from the ulcer 1 hour after the wound was cleaned and dressed indicates purulent exudate.	
Sanguinous exudates Bloody fluid that's present on a dry gauze dressing removed from the ulcer 1 hour after the wound was cleaned and dressed indicates sanguinous exudate.	
Serous exudates Thin, watery fluid that's present on a dry gauze dressing removed from the ulcer 1 hour after the wound was cleaned and dressed indicates serous exudate.	
Delayed healing of the ulcer The patient reporting no change, or increase in the volume or surface area of the ulcer, over the preceding 4 weeks indicates delayed healing. Ask the patient if the ulcer has filled with tissue or is smaller around than it was 4 week ago.	
Discoloration of granulation tissue Granulation tissue that is pale, dusky, or dull in color compared to surrounding, health tissue. Note variations of normal, beefy-red appearance of granulation tissue.	
Friable granulation tissue Bleeding of granulation tissue when gently manipulated with a sterile cotton-tipped applicator indicates friable tissue.	
Pocketing at base of wound The presence of smooth, nongranulating pockets of ulcer tissue surrounded by beefy red granulation tissue indicates pocketing.	
Foul odor The ulcer may have a putrid or distinctively unpleasant smell	
Wound breakdown Small open areas in newly formed epithelia tissue not caused by reinjury or trauma indicate wound breakdown.	

[Reference: Sharon Baranoski, Elizabeth A. Ayello, Wound Care Essentials: Practice Principles]

12.2.7 Adverse events

Treatment-emergent adverse events will be identified during the study by the investigator's medical care, such as an interview and medical examination by interview, and the onset and resolution dates, intensity and outcome of the adverse event, action taken for the study device and causal relationship with the study device, suspected drug/medical device other than the study device, and treatment of the adverse event and details will be recorded.

In addition, the following local adverse events at the target pressure ulcer will be separately recorded with a visual evaluation and medical examination by interview.

Local adverse events: Erythema, edema, itching, flare, rash, and others

12.2.8 Concomitant medication review

For drugs/treatment administered during the study, survey the dosing period, administered dose, administration frequency and reason for administration via a medical examination by interview, and record in the Case Report Form.

12.2.9 Self-dressing training and frequency review

As a subject is to perform dressing twice weekly by himself/herself or a guardian, the investigator (or clinical research coordinator) will train the subject or guardian on standard dressing for self-dressing at every visit. Depending on the condition of the pressure ulcer such as excessive exudates, a subject may conduct self-dressing more frequently than twice weekly. In case of conducting self-dressing beyond twice weekly, the subject should inform the investigator of the additional dressing frequency during the site visit, and the investigator will record the frequency of self-dressing beyond twice weekly in the Case Report Form.

Standard dressing method will be trained as follows.

- ① Carefully wash the target pressure ulcer with normal saline.
- ② After washing, wipe the study ulcer for drying with sterilized gauze, if necessary. In this process, pay attention not to irritate the study ulcer with the gauze.
- ③ Open packaging of the study device, take out the device using tweezers, and remove the release film. Directly cover the wound with the foam side without the release film, paying attention to completely cover the wound.
- ④ If necessary, fix around the edge of this product with surgical tape or Band-Aid while paying attention not to attach too tight to avoid skin irritation.
- ⑤ If there is a lot of exudate and a leak is likely to occur at the study ulcer, exchange the dressing more frequently than planned for self-dressing (once weekly).

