Pressure ulcer assessment ⁶ (digital photograph taking, investigator's photo evaluation) - Ulcer size (Using a scale) - Complete healing status	V ⁷	V	V	V	V	V	V	V	V	V	V	V	V	V	V	V	V	V	V	V	V	V	V	V	V	V

Item	Schedule	Screening		Treatment period																		Closing					
		1*	2*	3	4	5	6	7	8	9	10	11	12	13	14**												
		-14d~0d	1d (±1d)	5d* (±1d)	8d (±1d)	12d* (±1d)	15d (±1d)	19d* (±1d)	22d (±1d)	26d* (±1d)	29d (±1d)	33d* (±1d)	36d (±1d)	40d* (±1d)	43d (±1d)	47d* (±1d)	50d (±1d)	54d* (±1d)	57d (±1d)	61d* (±1d)	64d (±1d)	68d* (±1d)	71d (±1d)	75d* (±1d)	78d (±1d)	82d* (±2d)	85d (±2d)
PUSH		V			V				V				V				V			V							V
Self-dressing training		V		V	V	V	V	V	V	V	V	V	V	V	V	V	V	V	V	V	V	V	V	V	V	V	V
Dressing change frequency review				V	V	V	V	V	V	V	V	V	V	V	V	V	V	V	V	V	V	V	V	V	V	V	V
Infection sign checklist ⁸ (CSSC)		V		V	V	V	V	V	V	V	V	V	V	V	V	V	V	V	V	V	V	V	V	V	V	V	V
Subject diary distribution ⁹		V		V	V	V	V	V	V	V	V	V	V	V	V	V	V	V	V	V	V	V	V	V	V	V	V
Subject diary return				V	V	V	V	V	V	V	V	V	V	V	V	V	V	V	V	V	V	V	V	V	V	V	V
Concomitant medication/treatment review	V	V		V	V	V	V	V	V	V	V	V	V	V	V	V	V	V	V	V	V	V	V	V	V	V	V
Adverse event review		V		V	V	V	V	V	V	V	V	V	V	V	V	V	V	V	V	V	V	V	V	V	V	V	V

* Visit 1 and Visit 2 can take place on the same day.

** Subjects who have complete healing during the study or are withdrawn from the study will have all tests scheduled for V14.

¥ Subject do not make a site visit but perform self-dressing.

† Except for Randomization visit, Home Health Care system through study coordinator will be used for those subjects who aren't able to make a visit during the treatment period. Physical examination and measuring weight may be exempt in case of replacing visit with Home Health Care.

- Blood pressure, pulse, body temperature measurement
- Laboratory tests: If test findings within 2 weeks prior to the consent date are available, they may be used instead of screening findings.
 - Hematology: WBC, RBC, platelet, WBC count, Hb, Hct
 - Blood chemistry: AST, ALT, ALP, creatinine, BUN, total bilirubin, glucose, protein, albumin, gamma GTP, TSH (TSH is conducted at screening only)
- Urine hCG pregnancy test is conducted only in women of child-bearing potential.
- The investigational device is changed twice weekly; additional changes are allowed depending on the pressure ulcer condition, without any limitation to frequency.

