10.1 Study design

[figure not shown]
This is a single-center, randomized, 2-arms, open-label pilot study.

Subjects who consent to the study will be assessed for eligibility with screening tests. Subjects can have a 2-week screening period.

After screening, subjects who meet the inclusion/exclusion criteria will apply Medifoam[®] or Betafoam[®] for 12 weeks, after randomization. Targeted subjects are outpatient clinic or hospitalized patients. Subjects will make once weekly site visits.

During the treatment period, dressing is performed twice weekly, but additional dressing changes are allowed, depending on the condition of the pressure ulcer, such as excessive exudates at the study ulcer. Nevertheless, the frequency of additional dressing is limited to twice per day. On the weekly site visit days, the investigator (or clinical research coordinator) will change the dressing; on other occasions, the subject or guardian will perform self-dressing. Subjects who achieve complete healing of the target pressure ulcer within 12 weeks will have early completion.

Efficacy assessment is conducted for a total of 12 times at a 1-week interval, after the investigational device application (8d, 15d, 22d, 29d, 36d, 43d, 50d, 57d, 64d, 71d, 78d, 85d). At each efficacy assessment, the investigator (or clinical research coordinator) should take a digital photograph of the target pressure ulcer and retain it as a source document.

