10.2 Investigational device application methods

[Investigational devices]

Medifoam[®] (Mundipharma)

Betafoam[®] (Mundipharma)

[General investigational device application method]

An appropriate type of the investigational device should be selected for the study ulcer size and it should be able to completely cover the target pressure ulcer. At every dressing change, record the selected investigational device size in the source document.

[Investigational device application sequence]

- ① Carefully wash the target pressure ulcer with normal saline.
- ② After washing, wipe the study ulcer for drying with sterilized gauze, if necessary. At this time, pay attention not to irritate the study ulcer.
- ③ Select a study device that is larger than the pressure ulcer, open the product packaging, take out the device using tweezers, and remove the release film. Directly cover the wound with the foam side without the release film, paying attention to completely cover the wound.
- ④ If necessary, fix around the edge of this product with surgical tape or Band-Aid while paying attention not to attach too tight to avoid skin irritation.
- ⑤ If there is a lot of exudate and a leak is likely to occur at the study ulcer, exchange the dressing more frequently than planned (twice weekly).

[Application frequency]

- Twice weekly

During the 12-week treatment period, dressing is performed twice weekly, but additional dressing changes are allowed, depending on the condition of the pressure ulcer, such as excessive exudates at the lesion. Nevertheless, the frequency of additional dressing is limited to twice per day. In case of additional dressing changes beyond twice weekly changes, the change frequency should be recorded in the Case Report Form.

On the weekly site visit days, the investigator (or clinical research coordinator) will change the dressing; on other occasions, the subject or guardian will perform self-dressing. The investigator (or clinical research coordinator) will train the subject or guardian on the dressing method at every visit.

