12.1.2 Visit 2 (enrollment, 1d)

Subject enrollment will take place at the second visit, and the following assessment will be conducted.

- ① Conduct the physical examination.
- ② Review the inclusion/exclusion criteria, and subjects who are finally determined eligible will go through the process of randomization.

- ③ Before applying the investigational device, check the infection signs using the CSSC(Clinical Signs and Symptoms Checklist).
- ④ Before applying the investigational device, take a photograph of the study ulcer, investigator will conduct a photo evaluation, and record the pressure ulcer size by a Scale.
- ⑤ After conducting standard dressing, apply the investigational device.
- ⑥ Record the baseline PUSH score.
- ⑦ Review concomitant medication and treatment-emergent adverse events.
- ⑧ Prescribe the investigational devices and train the subject or guardian on the self-dressing method.
- ⑨ Dispense the subject diary to record the frequency of position changes per day (if applicable) and the frequency of additional self-dressing.

12.1.3 Visit 3, 4, 5, 6, 7, 8, 9, 10, 11, 12, 13 (interim visit, 8d, 15d, 22d, 29d, 36d, 43d, 50d, 57d, 64d, 71d, 78d)

The following tests will be conducted at the interim visit. It can be replaced by home health care through coordinator's visit if the subject is not able to visit the institution.

- ① Conduct the physical examination.
- ② As vital signs, measure blood pressure, pulse, and body temperature.
- ③ Measure body weight (only 29d).
- ④ After removing the investigational device, take a photograph of the study ulcer, conduct the investigator's photo evaluation, and record the pressure ulcer size by a Scale and complete healing status.
- ⑤ Check the infection signs using the CSSC (Clinical Signs and Symptoms Checklist).
- ⑥ After conducting standard dressing, apply the investigational device.
- ⑦ After conducting the pressure ulcer assessment, record the PUSH score (15d, 29d, 43d, 57d, 71d).
- ⑧ Review concomitant medication and adverse events (all adverse events, local adverse events at the study ulcer).
- ⑨ Prescribe the investigational devices and train the subject or guardian on the self-dressing method.
- ⑩ At the last visit, investigational devices that have been prescribed but not used are to be returned.
- ⑪ Based on the subject diary, record the frequency of self-dressing beyond once-weekly in the Case Report Form.

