12.1.4 Visit 14 (End-of-Study visit/85d or early completion)

The following tests will be conducted at the End-of-Study visit or early completion (only in subjects with complete healing).

- ① Conduct the physical examination.
- ② As vital signs, measure blood pressure, pulse, and body temperature.
- ③ Measure body weight.
- ④ Conduct laboratory tests (hematology, blood chemistry).
- ⑤ After removing the investigational device, take a photograph of the study ulcer, conduct the investigator's photo evaluation, and record the pressure ulcer size by a Scale and complete healing status.
- ⑥ Check the infection signs using the CSSC (Clinical Signs and Symptoms Checklist).
- ⑦ Conduct standard dressing.
- ⑧ After conducting the pressure ulcer assessment, record the PUSH score.
- ⑨ Review concomitant medication and adverse events (all adverse events, local adverse events at the study ulcer).
- ⑩ At the last visit, investigational devices that have been prescribed but not used are to be returned.
- ⑪ Based on the subject diary, record the frequency of self-dressing beyond once-weekly in the Case Report Form.

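### Protocol 12.2.9 sets self-dressing and its CRF trigger at twice weekly where the rest of the protocol has once weekly, and SAP 7.1 counts the same endpoint beyond twice daily instead of twice weekly

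*Protocol*

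**What the plan says.** **Planned regimen.** Protocol 10.1 and 10.2 plan two dressing changes per week in total. Staff do one of them: "On the weekly site visit days, the investigator (or clinical research coordinator) will change the dressing". The schedule of study activities marks one day between consecutive visits (5d, 12d and so on to 82d) with the note "Subject do not make a site visit but perform self-dressing".

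**Recording at visits.** Protocol 12.1.3 (Visits 3 to 13) tells the site to "record the frequency of self-dressing beyond once-weekly in the Case Report Form", and 12.1.4 (Visit 14) repeats the instruction. Section 10.2 states the same rule for the total: "In case of additional dressing changes beyond twice weekly changes, the change frequency should be recorded in the Case Report Form".

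**Section 12.2.9.** The opening paragraph begins "As a subject is to perform dressing twice weekly by himself/herself or a guardian" and ends "the investigator will record the frequency of self-dressing beyond twice weekly in the Case Report Form". It uses twice weekly four times: once for the planned frequency and three times as the threshold for extra changes. Step 5 of the dressing method in the same section reads "exchange the dressing more frequently than planned for self-dressing (once weekly".

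**Endpoint definition.** Protocol 15.3 defines dressing change frequency as the changes made in addition to two per week. SAP 7.1 defines it as those in addition to two per day. The SAP shells for Tables 0702 and 0703 tabulate changes per week. The dressing paragraph of the synopsis asks for a CRF entry only when the limit of two additional changes per day is exceeded.

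**The concern.** Two rules for one endpoint give a wrong count if they are followed as written.

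The first lies in data collection. A site that applies the opening paragraph of 12.2.9 does not record the first extra home change in any week that has one. A site that trains subjects to its first sentence also doubles the planned home changes.

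The second lies in the analysis. Under SAP 7.1 as written, any subject who never exceeds two changes in a day scores zero, however many extra changes were made over the week. The endpoint exists to capture extra changes prompted by exudate or the state of the ulcer, and those are the changes lost.

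SAP 8 compares this endpoint between Medifoam and Betafoam with Fisher's exact test, although protocol 16.2 plans no formal test. If every subject scores zero, there is nothing to compare.

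**Working it through.** **Reproducing the planned regimen.** Staff apply the device on 1d, 8d, ..., 78d, which is 12 changes. The home days are 5d, 12d, 19d, 26d, 33d, 40d, 47d, 54d, 61d, 68d, 75d and 82d, also 12. The total is 24 over 12 weeks, and 24 / 12 = 2 per week, as 10.2 states. One of the two is at home. The first sentence of 12.2.9, read literally, gives 2 × 12 = 24 home changes instead of 12.

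**Counting extras.** Let *h* be the home changes per week, with one staff change per week for 12 weeks.

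- 10.2 and 15.3 (total beyond two per week): 12 × (*h* + 1 − 2) = 12 × (*h* − 1).
- 12.1.3 and 12.1.4 (self-dressing beyond one per week): 12 × (*h* − 1), the same count.
- 12.2.9, opening paragraph (self-dressing beyond two per week): 12 × max(*h* − 2, 0).
- SAP 7.1 (changes above two on a day): 0 unless some day has more than two changes.

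| Home changes per week | Total per week | 10.2, 15.3, 12.1.3, 12.1.4 | Literal 12.2.9 | Literal SAP 7.1 |
|---|---|---|---|---|
| 1 (as scheduled) | 2 | 0 | 0 | 0 |
| 2 | 3 | 12 | 0 | 0 |
| 3 | 4 | 24 | 12 | 0 |
| 4 | 5 | 36 | 24 | 0 |
| 6 (one change every day) | 7 | 60 | 48 | 0 |
| 13 (two changes every day) | 14 | 144 | 132 | 0 |

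The SAP 7.1 column assumes that no day has more than two changes. For any constant *h* of 2 or more, 12.2.9 records 12 fewer than the other protocol sections.

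**Effect in the planned tables.** Tables 0702 and 0703 have weekly rows from None to Four or more times and do not say whether they count extras or totals.

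- If extras: the correct row against the 12.2.9 row is One against None at *h* = 2, Two against One at 3, Three against Two at 4, and Four or more against Three at 5. At 6 or more, both fall in the top row.
- If totals (two plus the recorded extras): the row is Three against Two at *h* = 2 and Four or more against Three at 3. From 4 upwards both fall in the top row.

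**The case against.** The strongest reply is that the rest of the protocol largely covers the site risk. Sections 12.1.3, 12.1.4 and 10.2 each require the extra change to be recorded, and 12.2.12 has the diary capture self-dressing. The first sentence of 12.2.9 may be a loose restatement of the total regimen. The SAP slip probably echoes the daily limit in SAP 3. It may not survive programming, since the shells are weekly and SAP 11 says the analysis follows the protocol in principle. The figure of 12 against 0 needs exactly two home changes in every week for all 12 weeks, and early healing or withdrawal shortens the count. No planned table shows a 12-week total, and the shells have no p-value column.

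Most of this stands as a limit on size. It does not remove the conflict. The CRF sentence in 12.2.9 refers explicitly to self-dressing, so reading the paragraph as the total regimen does not rescue it. The diary is a partial safeguard: 12.2.12 says it holds self-dressing frequency, while note 9 to the schedule and the visit instructions say only the additional frequency. If subjects are taught that additional means beyond two home changes, the lost change may not be in the source. SAP 11 does not correct the definition in SAP 7.1.

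A further objection is that replacing the synopsis trigger drops the record of changes above the daily limit. It does not, because recording every change beyond two per week includes those.

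**Conclusion.** The concern holds. The opening paragraph of 12.2.9 is the outlier within the protocol: its own step 5, 12.1.3, 12.1.4, 10.2, 15.3 and the 12 scheduled home days all agree on one staff and one home change per week. SAP 7.1 conflicts with protocol 15.3 and with the SAP's own weekly shells.

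Following 12.2.9 loses one extra change in each week with two or more home changes, up to 12 per subject over a full 12 weeks. In the weekly tables this is a shift of at most one row. Following SAP 7.1 removes every extra unless a day has more than two changes, so 144 becomes 0 at two changes every day.

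These totals assume the same pattern each week and a full 12 weeks on treatment; the documents give no rate of extra changes. A subject on the scheduled regimen scores 0 under every rule. No endpoint of main interest and no safety analysis depends on this count. It should be corrected, as a matter of consistency in an exploratory endpoint.

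**What to change.** - **Protocol 12.2.9, opening paragraph:** change twice weekly to once weekly in all four places, so that the planned self-dressing and the CRF trigger match step 5, 12.1.3 and 12.1.4.
- **SAP 7.1:** change the daily threshold to the weekly one in protocol 15.3.
- **Protocol synopsis, dressing paragraph:** replace the CRF trigger with the 10.2 rule, so that changes beyond two per week are recorded.

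The cost is a few words in two places of the protocol and one in the SAP. The protocol changes need IRB approval under 21.2. No visit or staff is added, and the text asks for no new form field because 10.2, 12.1.3 and 12.1.4 already require the entry. The CRF and diary forms were not available to check, so the sponsor should confirm that neither carries the wrong threshold. Any subject or guardian already trained to two home changes per week needs re-instruction at the next weekly visit.

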12.2.10 Prescription of the study device

For a subject's self-dressing, the study devices will be prescribed at every visit from Visit 2 (1d), and unused medical devices are to be brought to the site at the next visit.

